10.2 Analysis Conventions

10.2.1 Analysis Sets

10.2.1.1 *Efficacy*

The analysis set for antiviral activity analyses will be subjects who were enrolled into the study and received at least one dose of study drugs.

10.2.1.2 *Safety*

The primary analysis set for safety analyses will include subjects who received at least one dose of study drug.

Treatment-emergent data will be analyzed and defined as data collected from the first dose of study drug through the date of last dose of study drug plus 30 days.

10.3 Data Handling Conventions

Missing data can have an impact upon the interpretation of the trial data. Other than the endpoints discussed below, values for missing data will not be imputed.

For the analysis of post-baseline categorical efficacy endpoints, if a data point is missing and is preceded and followed in time by values that are deemed successes, then the missing data point will be termed a success; otherwise the data point will be termed a failure.

Any subject with missing data due to premature discontinuation of the study drug will be considered a failure at the date of premature discontinuation and all time points subsequent to the date of premature discontinuation if there are no observed values available. If no HCV RNA values are obtained after the last dose of study drug, the subject will be considered a treatment failure for the SVR endpoints.

Where appropriate, safety data for subjects that did not complete the study will be included in summary statistics.

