5.4 HCV Virologic Response-Based Treatment Stopping Criteria

Treatment will be stopped if there is a less than 1 log₁₀ decline in HCV RNA after 4 weeks of therapy.

Confirmation should be performed as soon as possible and must occur no later than 2 weeks after an initial observation indicating virologic failure. All subjects who terminate treatment early will complete the Early Termination (ET) Visit, Week 4 and Week 12 Post-Treatment Visits.

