5.5 Treatment Discontinuation Criteria

The Medical Monitor should be consulted prior to subject discontinuation when medically feasible. Study drug must be discontinued in the following instances:

- Unacceptable toxicity, as defined in Section 9 of the protocol, or toxicity that, in the judgment of the Sponsor-Investigator or Sub-Investigator(s), compromises the ability to continue study-specific procedures or is considered to not be in the subject's best interest
- Pregnancy of female subject
- HCV efficacy failure as defined in Section 5.3
- Significant protocol violation
- Subject request to discontinue for any reason; it is important to determine and document whether the withdrawal of consent is primarily due to an adverse event (AE), lack of efficacy, or other reason
- Discontinuation of the study at the request of CRI, regulatory agency, or an Institutional Review Board (IRB)/Independent Ethics Committee (IEC)

If a subject meets discontinuation criteria during treatment, an Early Termination Visit will be required (Section 8.2.4). Early Termination Visits should be scheduled as soon as possible following discontinuation of treatment. Subjects that discontinue treatment early are still required to complete Post-Treatment Weeks 4, and 12 Visits.

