7.3 Prior and Concomitant Medications

Concomitant medications taken within 30 days prior to screening, up to and including 30 days after the last dose of study drug, need to be recorded in the source documents and case report form(s) (CRFs).

The following medications are prohibited during the screening period and for a minimum of 28 days prior to the Baseline/Day 1 Visit through the end of study:

- Proton pump inhibitors (other than omeprazole 20 mg as below)
- Amiodarone
- Digoxin
- Carbamazepine
- Phenytoin
- Phenobarbital
- Oxcarbazepine
- Rifabutin
- Rifampin
- Rifapentine
- Efavirenz

- Tipranavir/ritonavir
- Sofosbuvir as a single agent
- St. John's wort, echinacea, milk thistle
- Rosuvastatin at a dose exceeding 10 mg
- Atorvastatin at a dose exceeding 20 mg

The following medications will be used with caution during the study:

Velpatasvir solubility decreases as pH increases. Drugs that increase gastric pH are expected to decrease the concentration of velpatasvir. Therefore, patient who are currently on acid lowering therapy including Antacids (Tums, Mylanta, Maalox, Rolaids etc.), Famotidine/Pepcid, Ranitidine/Zantac, Esomeprazole/Nexium, Omeprazole/Prilosec, Lansoprazole/Prevacid, Pantoprazole/Protonix and who must continue acid lowering therapy must agree to one of the three acid lowering treatment regimens.

- Tums as needed separated from Epclusa by at least 4 hours
- Zantac at a dose no higher than 150 mg once daily to be separated from Epclusa by 12 hours
- Omeprazole at a dose no higher than 20 mg once daily. For patients on omeprazole, Epclusa must be taken with food 4 hours prior to omeprazole dosing.

Renal function should be monitored in patients taking tenofovir DF with Epclusa.

Epclusa increases levels of the HMG-CoA reductase inhibitors, rosuvastatin and atorvastatin. Patients on atorvastatin and rosuvastatin should be monitored closely for evidence of myopathy. The dose of rosuvastatin should not exceed 10 mg and the dose of atorvastatin should not exceed 20 mg.

Medications for disease conditions excluded from the protocol (e.g., active cancer, transplantation) are not listed under this Concomitant Medication section and are disallowed in the study.

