10.1.2 Primary Endpoint

The primary efficacy endpoint is rate of SVR-12 (HCV RNA <LLOQ 12 weeks after discontinuation of study treatment).

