10.5 Primary Analysis

The primary efficacy endpoint is SVR-12 (HCV RNA < LLOQ 12 weeks after discontinuation of study treatment). The percent of patients achieving SVR-12 and its 95% confidence interval of SVR-12 will be reported.

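### The SVR12 rules place no condition on non-study anti-HCV therapy, so a subject who stops Epclusa early, switches regimen and is below LLOQ at post-treatment week 12 is scored a success, and a switch after day 30 may go unrecorded

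*Combined protocol and SAP*

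**What the plan says.** **Endpoint.** Section 10.1.2 reads: "The primary efficacy endpoint is rate of SVR-12 (HCV RNA <LLOQ 12 weeks after discontinuation of study treatment"). Section 10.5 repeats the definition and adds that the percentage and its 95% confidence interval will be reported. Neither section sets a condition on other anti-HCV therapy.

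**Who is analysed.** The efficacy set in 10.2.1 is "subjects who were enrolled into the study and received at least one dose of study drugs", so early stoppers stay in the denominator.

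**Follow-up of early stoppers.** Section 5.4 states: "All subjects who terminate treatment early will complete the Early Termination (ET) Visit, Week 4 and Week 12 Post-Treatment Visits". Section 5.5 says the same for its own discontinuation criteria: "Subjects that discontinue treatment early are still required to complete Post-Treatment Weeks 4, and 12 Visits". Appendix 2 schedules HCV RNA at both post-treatment visits.

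**Missing data.** Under 10.3, a subject with missing data because of premature discontinuation is a failure from that date and at "all time points subsequent to the date of premature discontinuation if there are no observed values available". A second rule, for the SVR outcomes, reads: "If no HCV RNA values are obtained after the last dose of study drug, the subject will be considered a treatment failure for the SVR". Both apply only when values are absent.

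**Medication data.** Section 7.3 requires recording of "Concomitant medications taken within 30 days prior to screening, up to and including 30 days after the last dose of study drug". In Appendix 2 the medication review is marked from screening to the end-of-treatment or early-termination visit and at unscheduled visits. It is blank for post-treatment weeks 4 and 12, and 8.4.1 does not list it. Section 8.5 collects medications at any unscheduled visit. The list in 7.3 of drugs prohibited to the end of the study names one anti-HCV drug, single-agent sofosbuvir.

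**The concern.** The primary objective is the effectiveness of Epclusa given by psychiatrists in an addiction clinic. A subject who came off Epclusa for poor week 4 response, toxicity or personal choice, and whose virus was then suppressed by a different regimen, is not evidence of that effectiveness. Read literally, the plan still scores the subject as a success. This error can only raise the reported rate.

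The data to correct it may also be lacking. Required recording stops well before the endpoint sample, and nobody is scheduled to ask about medications at the visit where that sample is drawn. If a case did come to light, its handling would have to be decided after the result was known.

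**Working it through.** The plan gives no power calculation, target rate or success threshold, so it has no figure of its own to reproduce. The check is on the text, the dates and the effect on the reported percentage.

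**1. Scoring path for an early stopper who switches regimen**
- At least one dose taken: in the efficacy set (10.2.1).
- Post-treatment weeks 4 and 12 still required (5.4, 5.5), so a week 12 HCV RNA is expected.
- Week 12 value missing: 10.3 makes the subject a failure, because nothing is observed at or after that point.
- Week 12 value observed and quantifiable: failure by the endpoint definition (10.1.2, 10.5).
- Week 12 value observed and below LLOQ: success by the same definition. No section overrides this for a change of regimen.

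Only the last branch goes wrong.

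**2. Recording gap**
- Endpoint sample: 12 × 7 = day 84 after the last dose. With the ±5 day window in 8.4.1, days 79 to 89.
- Required recording ends at day 30 (7.3).
- Gap: 84 − 30 = 54 days (79 − 30 = 49 to 89 − 30 = 59).
- Share of the 84 days: 54/84 = 64%. The first 30 days, 30/84 = 36%, are covered by 7.3.
- Even the covered part has no scheduled review after the end-of-treatment or early-termination visit (Appendix 2), so 7.3 and the procedures table do not fully match.

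**3. Effect on the reported result**

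With n = 20 (Section 5.1, approximate), one subject is 1/20 = 5 percentage points. Section 10.5 does not name an interval method. Exact (Clopper-Pearson) limits are used here: lower = Beta quantile at 0.025 with parameters (x, n − x + 1), upper = Beta quantile at 0.975 with (x + 1, n − x). For x = n = 20 the lower limit reduces to 0.025^(1/20) = 0.832.

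| Successes | SVR12 | Exact 95% CI |
|---|---|---|
| 20/20 | 100% | 83.2 to 100% |
| 19/20 | 95% | 75.1 to 99.9% |
| 18/20 | 90% | 68.3 to 98.8% |

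**4. How often**

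The documents give no rate of switching. The chance of at least one such subject among 20 is 1 − (1 − p)^20 for a per-subject rate p:

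| Assumed p | Chance of at least one in 20 |
|---|---|
| 0.2% | 3.9% |
| 1% | 18.2% |
| 5% | 64.2% |
| 10% | 87.8% |

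The 0.2% is borrowed from Section 3.2, where it is the rate of stopping for adverse events in the cited Phase 3 trials. It is not a switching rate. The other values are assumptions that show the range.

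**The case against.** The best defence is that this is silence, not a bad rule, and that the event is rare. The sentence in 10.3 is a missing-data convention and does not address values observed after a switch. Sections 5.4 and 5.5 already speak of failure for subjects stopped for poor response. A misclassified case needs an early stop, a new regimen begun within 84 days, an attended week 12 visit and RNA below LLOQ. Section 3.2 reports few adverse-event stops and SVR12 of 89% to 100% across the tabulated groups. Section 3.1 describes limited access to HCV treatment in this population, which weighs against quick re-treatment. The trial is a single-arm pilot with no test or threshold.

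Much of this stands. The gap is an omission, and the number affected may well be zero. But the failure language in 5.4 and 5.5 is not linked to SVR12 scoring, so the literal result is unchanged. Having no threshold does not help either, because the percentage and its interval are themselves the primary result.

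A reader might also draw stronger conclusions that the documents do not support:
- **That a switch could never be detected.** A start within 30 days of the last dose must be recorded (7.3), and unscheduled visits collect medications (8.5). Subjects are existing patients of one clinic, so staff may also know. Still, no rule uses a switch that is recorded.
- **That the second regimen's cure is credited to Epclusa.** A sample at day 84 could show suppression on a regimen started after Epclusa stopped. It could not show a 12-week sustained response to it.
- **That 64% of the risk is hidden.** The figure is a share of days. Starts shortly before day 84 leave little time for RNA to fall below LLOQ.
- **That SVR4 needs the same rule.** SVR4 is not among the endpoints in 10.1.

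**Conclusion.** The point holds as a gap in the definition of the primary endpoint. Sections 10.1.2, 10.3 and 10.5 would score a subject who stopped early, switched regimen and had an observed week 12 RNA below LLOQ as an SVR12 success. Starts from about day 31 to day 84 may go unrecorded unless an unscheduled visit captures them. Each such subject is worth 5 points if 20 are dosed, always in the favourable direction. The frequency is unknown and probably low, so the expected effect on the reported rate is small. The conclusion rests on a literal reading of the endpoint text and on early stoppers attending the week 12 visit that the protocol requires. This is a cheap improvement; it does not put the trial's design in doubt.

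**What to change.** - **Sections 10.3 and 10.5:** state that a subject who starts any non-study anti-HCV drug before the post-treatment week 12 HCV RNA sample is an SVR12 failure, whatever value is observed.
- **Section 7.3, Section 8.4.1 and the post-treatment column of Appendix 2:** record the name and start date of any anti-HCV drug through post-treatment week 12.

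This concerns scoring and data capture only and changes no patient's treatment. It costs one sentence in the analysis text, one added question at visits already scheduled, and a possibly slightly lower SVR12. In return, the handling of any such case is fixed before the results are known.

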10.4 Demographic Data and Baseline Characteristics

Demographic data will include sex, self-identified race, self-identified ethnicity, and age.

Baseline characteristic data will include HCV RNA level, calculated FIB-4 index, and Fibrosis Score on FibroSure®. Demographic and baseline characteristics will be summarized using descriptive statistics: means and standard deviations for continuous characteristics such as age and frequencies/percentages for categorical measures such as sex and race. HCV RNA level will be reported as the categories “below LLOQ” or “detectable.”

10.5 Primary Analysis

The primary efficacy endpoint is SVR-12 (HCV RNA < LLOQ 12 weeks after discontinuation of study treatment). The percent of patients achieving SVR-12 and its 95% confidence interval of SVR-12 will be reported.

10.6 Secondary Analysis

Adherence:

- Percentage of patients who miss 1-4% of doses, 5-9% of doses, and 10-20% of doses and > 20% of doses and the 95% confidence interval will be reported. The percentage of doses taken out of total doses prescribed will be reported with its 95% confidence interval.

Quality of Life:

- Mean in QOL scores from baseline to EOT will be reported with its 95% confidence interval.

Safety Analysis

- All safety data collected on or after the first dose of study drug administration up to 30 days after the last dose of study drug will be summarized. **All AE's of each level severity will be reported with the number and percent who experienced them. The number and percent of patients who stopped the study because of SAE's will be reported, with the 95% confidence interval.**

10.7 Other Analyses

The Internal Medicine Physician's change in comfort level with providing HCV care over course of study will be reported descriptively, with a graph of the comfort level on each of six areas of counseling at each time point measured. In addition, a qualitative description of the Internal Medicine Physician's experience with the training will be reported.

11 SPONSOR-INVESTIGATOR RESPONSIBILITIES

11.1 Good Clinical Practice

The Sponsor-Investigator will ensure that this study is conducted in accordance with the principles of the Declaration of Helsinki (as amended in Edinburgh, Tokyo, Venice, Hong Kong, and South Africa), International Conference on Harmonization (ICH) guidelines, or with the laws and regulations of the country in which the research is conducted, whichever affords the greater protection to the study subject.

The Sponsor-Investigator will ensure adherence to the basic principles of Good Clinical Practice, as outlined in 21 CFR 312, subpart D, "Responsibilities of Sponsors and Investigators", 21 CFR, part 50, and 21 CFR, part 56.

The Sponsor-Investigator and all applicable Sub-Investigators will comply with 21 CFR, Part 54, providing documentation of their financial interest or arrangements with Gilead, or proprietary interests in the investigational drug under study. This documentation must be provided prior to the Sponsor-Investigator's (and any Sub-Investigator's) participation in the study. The Sponsor-Investigator and Sub-Investigator(s) agree to file any change in reportable interests during the study and for 1 year following completion of the study per CRI SOPs. Study completion is defined as the date when the last subject completes the protocol-defined activities.

11.2 Institutional Review Board (IRB)/Independent Ethics Committee (IEC) Review and Approval

The Sponsor-Investigator will submit this protocol, informed consent form, and any accompanying material to be provided to the subject (such as advertisements, subject information sheets, or descriptions of the study used to obtain informed consent) to an IRB/IEC. The Sponsor-Investigator will not begin any study subject activities until approval from the IRB/IEC has been documented and provided as a letter to the Sponsor-Investigator.

Before implementation, the Sponsor-Investigator will submit to and receive documented approval from the IRB/IEC any modifications made to the protocol or any accompanying material to be provided to the subject after initial IRB/IEC approval, with the exception of those necessary to reduce immediate risk to study subjects.

11.3 Informed Consent

The Sponsor-Investigator is responsible for obtaining written informed consent from each individual participating in this study after adequate explanation of the aims, methods, objectives, and potential hazards of the study and before undertaking any study -related procedures. The Sponsor-Investigator must use the most current IRB/IEC-approved consent form for documenting written informed consent. Each informed consent (or assent as applicable) will be appropriately signed and dated by the subject or the subject's legally authorized representative and the person conducting the consent discussion, and also by an impartial witness if required by IRB/IEC of local requirements.

11.4 Confidentiality

The Sponsor-Investigator must assure that subjects' anonymity will be strictly maintained and that their identities are protected from unauthorized parties. Only subject initials, date of birth, another unique identifier (as allowed by local law) and an identification code will be recorded on any form submitted to the Sponsor-Investigator or IRB/IEC. NOTE: The Sponsor-Investigator must keep a screening log showing codes, names, and addresses for all subjects screened and for all subjects enrolled in the trial. Subject data will be processed in accordance with all applicable regulations.

The Sponsor-Investigator agrees that all confidential study information, including but not limited to the Investigator Brochure, this protocol, eCRF, the study drug, and any other study information, remain the sole and exclusive property of the Sponsor-Investigator during the conduct of the study and thereafter. This information is not to be disclosed to any third party (except employees or agents directly involved in the conduct of the study or as required by law). The Sponsor-Investigator further agrees to take all reasonable precautions to prevent the disclosure by any employee or agent of the study site to any third party or otherwise into the public domain.

11.5 Study Files and Retention of Records

The Sponsor-Investigator will maintain adequate and accurate records to enable the conduct of the study to be fully documented and the study data to be subsequently verified. These documents should be classified into at least the following two categories:

- Sponsor-Investigator's study file, and
- Subject clinical source documents.

The Sponsor-Investigator's study file will contain the protocol/amendments, CRF and query forms, IRB/IEC and governmental approval with correspondence, informed consent, drug records, staff curriculum vitae and authorization forms, and other appropriate documents and correspondence.

The required source data should include sequential notes containing at least the following information for each subject:

- Subject identification (name, date of birth, gender);
- Original, signed informed consent form with documentation that the consent was signed prior to initiating any study procedures;

- Documentation that subject meets eligibility criteria, i.e. history, physical examination, and confirmation of diagnosis (to support inclusion and exclusion criteria);
- Documentation of the reason(s) a consented subject is not enrolled
- Participation in study (including study number);
- Study discussed and date of informed consent;
- Dates of all visits;
- Documentation that protocol specific procedures were performed;
- Results of efficacy parameters, as required by the protocol;
- Start and end date (including dose regimen) of study drug, including dates of dispensing and return;
- Record of all adverse events and other safety parameters (start and end date, and including causality and severity);
- Concomitant medication (including start and end date, dose if relevant, dose changes);
- Date of study completion and reason for early discontinuation, if it occurs.

All clinical study documents will be retained by the Sponsor-Investigator until 2 years after the investigation is discontinued and regulatory authorities have been notified.

11.6 Case Report Forms

For each subject consented, an eCRF will be completed by an authorized study staff member whose training for this function is documented according to study procedures. eCRF will be completed within three days of the subject visit to enable the Sponsor-Investigator to perform central monitoring of safety data. Subsequent to data entry, a study monitor will perform source data verification for select data points in accordance with the monitoring plan within the EDC system. Original entries as well as any changes to data fields will be stored in the audit trail of the system. Prior to database lock (or any interim time points as described in the clinical data management plan), the Sponsor-Investigator will use his/her log in credentials to confirm that the forms have been reviewed, and that the entries accurately reflect the information in the source documents. The eCRF capture the data required per the protocol schedule of events and procedures. System-generated or manual queries will be issued to the investigative site staff as data discrepancies are identified by the monitor or internal CRI staff, who routinely review the data for completeness, correctness, and consistency. A read-only archive copy of the case report form will be stored in accordance with the records retention requirements outlined in Section 11.5.

Study data will be collected and managed using REDCap electronic data capture tools hosted by Boston Computing Network (Harris et al. 2009). REDCap (Research Electronic Data Capture) is a secure, web-based application designed to support data capture for research studies, providing: 1) an intuitive interface for validated data entry; 2) audit trails for tracking data manipulation and export procedures; 3) automated export procedures for seamless data downloads to common statistical packages; and 4) procedures for importing data from external sources. It satisfies HIPAA-Security guidelines and is 21 CFR Part 11 capable, with compliance assured by the Community Research Initiative Information Technology Department and Boston Computing Network. Data will be exported from REDCap to the statistician for statistical analysis will be de-identified.

